## **3 INVESTIGATIONAL PLAN**

### **3.1 General Schema of Study Design**

This is a prospective case-control study.

All participants who have not had a baseline sleep study performed within the prior 12 months to enrollment will undergo baseline polysomnography. For participants with OSAS, this will have been obtained as part of their clinical care unless they are referred via the CHOP PeRC system. In these cases, the baseline polysomnogram will be part of research simply to facilitate recruitment. Both OSAS and controls will then undergo cognitive and behavioral testing during wakefulness, and CBF testing during wakefulness and sleep at 3 time periods over 12 months approximately (figures 2 and 3). OSAS participants will also undergo a repeat baseline sleep study 6-12 weeks after clinical treatment to document improvement.

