##### **3.3.1.2 Control Subjects**

The study will include 7 total visits for controls: a baseline sleep study to ensure normalcy, three full days of cognitive and behavioral and CBF testing (baseline, 6 and 12 months), and three sleep studies with CBF testing (baseline, 6 and 12 months). A daytime visit and one night time visit may be scheduled during a 24-hour period if the participant and family wish so. Otherwise, they will be scheduled on separate days.

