**4.1.7 Visit 7: Nighttime, 12 months after adenotonsillectomy**

- CBF testing during sleep during hypercapneic ventilatory response
- Height and weight assessment

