**4.2.7 Visit 7 Nighttime, 12 months after Visit 1**

- Height/weight assessment
- CBF testing during sleep during hypercapnic ventilatory response

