**4.3 Monthly Telephone Calls**

- There will be telephone calls during each month that a visit into the hospital is not necessary (months 2, 3, 4, 5, 7, 8, 9, 10, 11) for retention purposes, as well as to assess for adverse events.

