**4.5 Subject Completion/Withdrawal**

Subjects may withdraw from the study at any time without prejudice to their care. They may also be discontinued from the study at the discretion of the Investigator for lack of adherence to study treatment or visit schedules, AEs, or due to inability to follow instructions and perform testing. The Investigator or the Sponsor (if applicable) may also withdraw subjects who violate the study plan, or to protect the subject for reasons of safety or for administrative reasons. It will be documented whether or not each subject completes the clinical study. If the Investigator becomes aware of any serious, related adverse events after the subject completes or withdraws from the study, they will be recorded in the source documents and on the CRF.

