### 8.3.2 Risk Assessment

**Polysomnography:** Not greater than minimal risk. No significant risks are encountered from polysomnography, which is a standard, noninvasive monitoring procedure. Sleeping away from home may be unsettling. To allay anxiety, the subject's parents/guardians will be allowed to stay overnight in the same room as the subject. The subjects may develop skin rashes as a result of adhesive tapes.

**Diffuse optical and correlation spectroscopy:** Not greater than minimal risk. The hybrid DOS/DCS instrument is considered a non-significant risk device. There has been experience at both CHOP and The Hospital of the University of Pennsylvania with the instrument, and there have been no AEs. Please see attached safety notes.

**Psychometric Testing:** Not greater than minimal risk. This testing is potentially stressful or anxiety-producing; these risks will be addressed by offering breaks from testing as needed and having examiners who are well-trained in testing children and adolescents. Testing will be conducted in an appealing and quiet private area with child-sized furniture.

**Hypercapnic challenge:** Not greater than minimal risk. During wakefulness, the measurement of carbon dioxide and hypoxic responses may make the participant feel short of breath, as if he/she was running. Rarely, the participant may have a headache or dizziness from increased carbon dioxide. This will go away quickly after the test or after coming off the mouthpiece. The subject can come off the mouthpiece if he/she is uncomfortable. During sleep, these tests may cause arousal; typically, the subject is unaware of the cause of the arousal, and rapidly returns to sleep. If the participant is uncomfortable, s/he simply needs to remove the mask in order to breathe room air. The test will be stopped if the subject has frequent arousals, defined as waking from sleep more than 3 times during the hypercapnic challenge). A physician will be present whenever CO2 is administered, and the subject's end-tidal and transcutaneous PCO2, arterial oxygen saturation, EKG and EEG will be continuously monitored. Sleep disruption from arousals may result in excessive daytime sleepiness, inattention and impaired vigilance the following day. These effects are transitory and resolve with a good night of sleep. (35) Therefore, participants should not take school tests the following day.

---

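### Visit 7 is the only CO2 challenge night with no later scheduled adverse-event contact; one closing call would cover it

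*Combined protocol and SAP*

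**What the plan says.** Section 3.1 plans, for both groups, "CBF testing during wakefulness and sleep at 3 time periods over 12 months approximately". The last sleep session is "Visit 7: Nighttime, 12 months after adenotonsillectomy" for children with OSAS (section 4.1.7) and "Visit 7 Nighttime, 12 months after Visit 1" for controls (section 4.2.7). For the OSAS group its content is "CBF testing during sleep during hypercapneic ventilatory response", and the control entry is equivalent.

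The adverse-event row of Tables 1 and 2 has its last mark at that visit, and neither table has a later column. Section 4.3 states: "There will be telephone calls during each month that a visit into the hospital is not necessary". It then lists months 2 to 5 and 7 to 11.

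Section 4.5 limits recording after the study to the case "If the Investigator becomes aware of any serious, related adverse events after the subject completes or withdraws from the study".

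On the expected effects of a challenge night, section 8.3.2 says: "Sleep disruption from arousals may result in excessive daytime sleepiness, inattention and impaired vigilance the following day". It calls these effects short-lived and advises against school tests on that day. Section 7.1 promises AE monitoring for the duration of the study, and section 7.3 says that all AEs, serious or not, go into the study records and the case report form. No section states when AE collection ends.

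**The concern.** The protocol names effects that appear the day after a challenge night, and then places its last contact with the child on such a night. Once the child has completed, an event must be serious, related and known to the investigator before section 4.5 has it recorded. Sleepiness or inattention would normally be non-serious, so it falls outside that rule.

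What is at stake is even and complete ascertainment of the side effects of the study's own procedure. Two of the three challenge nights are followed by a scheduled occasion on which a parent can report them, and the third is not. The AE analyses sent to the DSMB (section 8.3.1) and the summaries sent to the IRB (section 7.2) would draw on that uneven record.

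**Working it through.** No formula in the plan bears on this point. The check is a count of nights and contacts.

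**Step 1: challenge nights per child.** Section 3.3.1.2 gives controls "three sleep studies with CBF testing (baseline, 6 and 12 months", that is, 3 nights. Counting the visits in sections 4.1 and 4.2 and in the tables reproduces this figure:
- OSAS: baseline (Visit 1), Visit 5, Visit 7 = 3
- Controls: Visit 3, Visit 5, Visit 7 = 3

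**Step 2: next scheduled AE contact after each night** (adverse-event rows of Tables 1 and 2, with section 4.3).

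| Group | Night | Next AE contact |
|---|---|---|
| OSAS | Visit 1 | Visit 2 (1 to 30 days after screening) |
| OSAS | Visit 5 | monthly call |
| OSAS | Visit 7 | none |
| Control | Visit 3 | monthly call |
| Control | Visit 5 | monthly call |
| Control | Visit 7 | none |

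No night has a contact fixed for the next day. The first two rely on recall at the next visit or call, possibly weeks later. What sets Visit 7 apart is that no later contact is scheduled at all.

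**Step 3: size.** Nights without a later contact, as a share of all nights, for *N* completers: *N* / (3 × *N*) = 1/3.
- 100 evaluable children (section 3.3.2): 3 × 100 = 300 nights, of which 100 have no later contact.
- All 140 enrolled complete: 3 × 140 = 420 nights, of which 140 have no later contact.

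Children who withdraw are outside this count. One who leaves after an earlier challenge night comes under the same section 4.5 rule, and section 4.5.1 offers only referral to clinical care, with no AE assessment.

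**Step 4: what this does to a rate.** Let *c1*, *c2*, *c3* be the share of true next-day effects that is recorded after nights 1, 2 and 3, and assume the true rate is the same on each night. The recorded share is (*c1* + *c2* + *c3*) / 3. It equals 2/3, an understatement of one third, only if *c1* = *c2* = 1 and *c3* = 0. The documents give none of these values. Raising *c3* to *c3\** by a closing call adds (*c3\** − *c3*) / 3, which is at most one third.

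**Step 5: after the change.** Nights followed by a scheduled AE contact rise from 2 of 3 to 3 of 3 per completer: 200 to 300 of 300, or 280 to 420 of 420.

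**The case against.** The strongest reply is that nothing in the protocol ends AE collection at Visit 7. The stop is inferred from the tables, the call months and section 4.5. An AE assessment is marked at Visit 7 without a time, so it could take place on the morning of discharge. Control families may pair a day and a night visit within 24 hours (section 3.3.1.2), in an unstated order, and a night-first pair would put the child in front of staff the next day. Other effects named in section 8.3.2, such as breathlessness, headache, dizziness and arousal, arise during or soon after the test, with a physician present. The next-day effects are disclosed and described as passing, and no endpoint or stopping threshold depends on counting them.

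Much of this stands, and it rules out four stronger readings that a reader might infer:
- *That the first two nights have next-day capture and only the third lacks it.* None has it (Step 2).
- *That the AE rate is understated by one third.* This needs full recall after the earlier nights and no capture after the last. It also concerns a per-night rate that the protocol does not plan to compute.
- *That effects of the last night cannot be recorded.* A discharge check or a night-first pair could catch some of them.
- *That the minimal-risk rating is undermined.* Sections 8.3.2 and 8.3.4 set that rating in advance, without using AE counts from this study.

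The reply does not remove the gap. A discharge check cannot cover the rest of that day, which is when daytime sleepiness and inattention would show. Pairing is optional, is stated only for controls, and runs against the numbering, which puts day Visit 6 before night Visit 7.

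**Conclusion.** The point holds as a low-severity gap in safety ascertainment. Visit 7 is the only one of each child's three challenge nights with no later scheduled AE contact. Non-serious next-day effects of that night are likely to be missed beyond any check at discharge, which sits poorly with section 7.3.

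Its size is 1 of 3 nights per completer: 100 of 300 for 100 completers, and up to 140 of 420 if all enrolled children complete. The count assumes that the tables and the call list are complete and that visits follow their numbering. It measures missing contacts, not missing events, because the documents give no rate for these effects. The primary endpoint, the sample size and the power do not change.

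**What to change.** Add one AE telephone contact shortly after Visit 7, for example within 7 days, as a last column in Tables 1 and 2 and in the call list of section 4.3. State that AE collection ends with that call, and align the meaning of completion in section 4.5 with it. Ask specifically about sleepiness, attention and vigilance on the day after the test. Put the same questions at the first contact after each earlier challenge night, so that all three nights are asked about in the same words. The recall interval will still be longer for some earlier nights, so record the date of each contact.

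The cost is about 100 to 140 short calls by staff who already make the monthly calls, plus the edits to the schedule. No new procedure or staff is needed.

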**4.5.1 Early Termination Study Visit**

Subjects who withdraw from the study will be referred for clinical care.

**5 STUDY EVALUATIONS AND MEASUREMENTS****5.1 Screening and Monitoring Evaluations and Measurements****5.1.1 Medical Record Review**

The following procedures will be performed:

- Demographics: age, gender, race

---

- Review of inclusion/exclusion criteria
- Previous PSG, if available.

### 5.1.2 Physical Examination

- Mallampati airway classification and tonsils size will be collected.
- Height
- Weight
- Vital signs

### 5.1.3 Other Evaluations, Measures

- **Baseline Polysomnography:**

Baseline polysomnography will be performed as part of the routine clinical evaluation of the subjects with OSAS prior to study entry (as per routine clinical practice), and as part of the research protocol in controls and OSAS subjects post-adenotonsillectomy. Overnight polysomnography will be performed in a dedicated pediatric sleep laboratory. The following parameters will be recorded (using Rembrandt, Medcare, Buffalo, NY): electroencephalogram, electrooculogram, submental and tibial electromyograms, chest and abdominal wall movement by inductance plethysmography (Respirtrace, Ambulatory Monitoring Inc., Ardsley, NY); ECG; airflow by nasal pressure (Pro-Tech, Mukilteo, WA) and 3-pronged thermistor (Pro-Tech), end-tidal PCO2 (Novametrix 7000; Novametrix, Wallingford, CT); arterial oxygen saturation (Masimo, Irvine, CA or Nonin, Plymouth, MN) and digital, infra-red video. The infra-red video is a component of any sleep study that is crucial for polysomnography interpretation as it provides information on breathing patterns, parasomnias, movements and seizures. The following parameters will be determined using standard pediatric techniques and scoring. (27). Any and all video recording will be in accordance with CHOP's policy on recording or filming patients.

1. Sleep architecture
2. Apneas and hypopneas
3. Arterial oxygen saturation (SpO2)
5. End-tidal carbon dioxide tension (ETCO2)

- Diffuse optical and correlation spectroscopy (DOS/DCS): The apparatus consists of light sources and detectors which are embedded in a rectangular black rubber pad that is strapped to the subject's head (similar to a pulse oximeter probe). The rectangular probe will be shielded from room light by a small disposable black cloth. For DOS, the static optical properties (absorption and reduced scattering coefficients) of the brain tissue will be measured using 110 MHz diffuse photon density waves at 690 and 830nm. From the absorption coefficients at these two wavelengths, we will obtain average cerebral oxygen saturation and total hemoglobin

---

concentration. Measurements will be made over the frontal cortex, and based on our probe geometry, light will penetrate approximately 0.5 cm into the brain. For DCS, the static optical properties will be measured by NIRS with 70 MHz diffuse photon density waves at 690, 786 and 830nm. Monitoring the absorption coefficient at the three wavelengths follows the hemoglobin saturations. Changes in CBF are obtained from correlation of decay times. The complete sets of source detector measurements provide both average values and local values of the tissue blood dynamics.

DOS/DCS is a non-significant risk device as defined by Food and Drug Administration (FDA) and therefore does not require FDA approval for investigational use. The device is used to collect data and is not being tested a part of the protocol. The instrument has been approved for laser and electrical safety by the University of Pennsylvania Environmental Health and Radiation Safety department and both CHOP and HUP clinical engineering departments for electrical safety. The optical imaging device will be used to record left and right hemispheric CBF, THC, and StO2. These three measurements will be performed continuously during the study time. The CBF measurements for each hemisphere (separately), THC and StO2 measurements from the last four minutes of each five minute recording interval will be averaged to avoid potential transient effects. This averaged number for right CBF, left CBF, and StO2 will be used in the statistical analysis.

- Ventilatory Response Testing during wakefulness: Ventilatory responses to hypercapnia will be determined using the rebreathing technique.(28-30) This is a standard clinical test. A physician will be present throughout the testing. Participants will sit quietly for 5-10 minutes before testing. Testing will be performed with the subject seated comfortably, watching a video, and breathing through a mouthpiece. Heart rate, SpO2 and end-tidal CO2 will be monitored continuously. Flow will be measured using a heated pneumotachograph connected to the mouthpiece and a differential pressure transducer. The actual test takes < 5 minutes but setup may take a total of about 30 minutes.
  - Ventilatory response to hypercapnia will be determined using the rebreathing technique of Read.(29) At the end of a normal expiration, a valve will be turned so that the subject will begin to breathe from a 13-liter bag. The bag will be filled with 70 ml/kg of a gas mixture with the initial composition of 95% O2 and 5% CO2. Each test will be continued until the subject cannot continue or end-tidal PCO2 reaches 65-70 mm Hg. Each test will be completed within 4-5 minutes to avoid prolonged respiratory acidosis. Tests will be discarded if the subject comes off the mouthpiece before the PCO2 reaches 55 mm Hg. Heart rate, SpO2, oximeter pulse waveform, and end-tidal PCO2 will be monitored continuously. The duration of this test is about 5 minutes.
- Ventilatory response testing during sleep: Subjects will wear a snug orofacial CPAP mask that will be attached to a heated pneumotachometer (Hans Rudolph, Kansas City, MO) and transducer (Validyne Engineering, Northridge, CA) and then to a T circuit. OSAS participants will receive an individualized positive pressure aimed at

---

treating obstructive sleep apnea and controls will receive a holding pressure of 2 cm H2O.(31) Room air will flow through the CPAP flow. ETCO2 will be measured via a port in the mask with an infrared capnometer (Novametrix 7000; Novametrix, Wallingford, CT). Transcutaneous CO2 (Radiometer, Paramus, NJ) will be continuously monitored during the study. A constant flow of CO2 will be introduced into the circuit at 5 l/min until the PCO2 reaches 65 mm Hg, the patient arouses, or for a maximum of 3 min, whichever occurs first. There will be no change in the total flow as air bias flow will be self-adjusted by the CPAP machine. Between challenges, subjects will breathe room air for a minimum of 15 min after the return of SpO2 and ETCO2 to baseline. Challenges will be primarily performed in slow-wave sleep (SWS); when possible, they will be repeated during stage 2 and rapid-eye-movement (REM) sleep. One trial will be attempted in each sleep stage. A physician will be in constant attendance at the bedside, and the patient's heart rate, respiration, and gas exchange will be closely monitored.

- Cognitive and Behavioral measures:
  - Participants will undergo the following testing:
    - Conners Continuous Performance Test-II (CPT-III)
    - Digit Span subtest of the Wechsler Intelligence Scale for Children, 4th Edition.
    - Tests of Everyday Attention for Children (TEA-ch)
    - Purdue Pegboard Test
    - Behavioral Rating Inventory of Executive Function -- Child Version (BRIEF-2)
    - Child Behavior Checklist
    - Epworth Sleepiness Scale Modified for Children
    - Adaptive Behavior Assessment System, Third Edition (ABAS-III)

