## 5.2 Safety Evaluation

During the sleep study, arterial oxygen saturation using pulse oximetry, transcutaneous carbon dioxide tension, EEG and EKG will be continuously monitored, and the patient will be visualized via a video camera.

During CBF measurements with ventilatory responses, heart rate, pulse oximetry, transcutaneous carbon dioxide tension, and end-tidal CO2 measurements will be continuously monitored and the patient will be directly visualized. A physician will be present whenever CO2 is administered.

---

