#### 6.4.2 Analysis of Primary Outcome of Interest

The primary analysis will include all subjects meeting all inclusion and exclusion criteria and completing all study visits.

The primary endpoint will be the change in CBF in OSAS and controls at baseline.

The secondary endpoint will be the change in CBF in OSAS and controls at 6 and 12 months after baseline measurements for controls and after adenotonsillectomy for OSAS.

Longitudinal models using generalized estimating equations (GEE) will be fitted to explore effects of treatment on CBF and NBT. An indicator variable for treatment, time, and a time by treatment group interaction term will be included in the models. If the interaction term

---

differs significantly from zero, this will indicate that the change over time in the outcome of interest differs significantly between the two groups. We will assess the sensitivity of results to the choice of working correlation structure that models association in the GEE analyses. We will also implement quasi-least squares (QLS), an approach based on GEE that allows for implementation of the Markov correlation structure.(32) The Markov structure is plausible if participants have unequal temporal spacing of their measurements. In addition, we will consider the application of mixed effects models if the assumptions of these models are met. An indicator variable for subjects who resolve after treatment versus those who do not resolve after treatment will be included in the model to account for those children whose OSAS may not resolve after surgery.(22, 33, 34) Pre-, post treatment change in AHI will be included in the model, and potential confounding variables such as age, gender, race, socio-economic status and BMI will also be included in the models.

Hypercapnic ventilatory responses will be controlled for BMI as obese participants may have different responses compared to non-obese participants.

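### The sleep CBF response is not defined so as to allow for the CO2 each child actually reached, so it mixes dose with reactivity

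*Combined protocol and SAP*

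**What the plan says.** **Stopping rule.** In section 5.1.3, CO2 enters the sleep circuit at a constant 5 l/min until PCO2 "reaches 65 mm Hg, the patient arouses, or for a maximum of 3 min, whichever occurs first". No minimum CO2 makes a sleep challenge valid. The awake test does have one: "Tests will be discarded if the subject comes off the mouthpiece before the" PCO2 gets to 55 mm Hg, and its target is 65–70 mm Hg. In sleep, "One trial will be attempted in each sleep stage". Section 8.3.2 expects early stops: "During sleep, these tests may cause arousal".

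**What is analysed.** Under the optical measurements in 5.1.3, "measurements from the last four minutes of each five minute recording interval will be averaged", and "This averaged number for right CBF, left CBF, and" StO2 goes forward to the statistics. Section 6.4.2 adds: "The primary endpoint will be the change in CBF in OSAS and controls at baseline". Its model terms are treatment, time, their interaction, resolution of OSAS, AHI change, and an open list of confounders (age, gender, race, socio-economic status, BMI). CO2 is not named. The one adjustment specific to hypercapnia is for BMI, and it concerns ventilatory responses.

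**What is monitored.** Section 5.2: "During CBF measurements with ventilatory responses, heart rate, pulse oximetry, transcutaneous carbon dioxide tension, and end-tidal" CO2 are followed continuously.

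**Pressure.** During sleep challenges OSAS children receive an individualised treating pressure and controls 2 cm H2O (5.1.3).

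**The concern.** Three alternative stopping rules and a fixed CO2 inflow do not deliver a common stimulus. Two children with identical reactivity will show different raw CBF changes if one wakes at 55 mm Hg and the other reaches 65. With one attempt per sleep stage, a short challenge is not replaced.

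Unequal doses add variance unrelated to reactivity, so power falls even when both groups are affected alike. If achieved CO2 also differed by group or visit, the comparison would be biased: earlier stopping in OSAS would imitate the blunted response that section 1.1 hypothesises, and earlier stopping in controls would hide it.

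The averaging rule adds a second problem. A challenge of at most 3 minutes cannot fill a four-minute average, so the plan has no workable definition of the sleep response. Sleep is in the synopsis primary objective, and the Abstract calls it the unknown question.

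**Working it through.** **1. The plan's own figure.** n = 50 per group, d = 0.566, two-sided alpha 0.05, t-test (6.5). The noncentral t gives power 0.800. The plan's 80% is reproduced and not disputed.

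**2. Averaging window.** If the four-minute average is applied to a sleep challenge, at most 3/4 = 75% of it is CO2 exposure, and less after an early arousal.

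**3. Effect of dose on one child.** Assume a linear response and baseline PCO2 of 40–45 mm Hg (the documents give no baseline). A challenge ending at 55 rather than 65 mm Hg yields (55−40)/(65−40) = 0.60 to (55−45)/(65−45) = 0.50 of the raw change.

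**4. Power with equal early stopping.** Assumptions, none from the documents except n and d:
- raw change = reactivity × CO2 rise + error, with mean control reactivity 1 and between-child CV 0.3–0.5
- baseline 42.5 mm Hg, so the rise is 22.5 (to 65) or 12.5 (to 55)
- 30% stop at 55 in both groups
- the true difference is 0.566 SD of reactivity.

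By hand, with CV 0.3 and no error:
- Mean rise = 0.7×22.5 + 0.3×12.5 = 19.5. Variance of rise = 0.3×0.7×10² = 21. Mean squared rise = 19.5² + 21 = 401.25.
- Group difference in raw change = 0.566×0.3×19.5 = 3.31.
- Variance in controls = 0.3²×401.25 + 21 = 57.1. In OSAS, mean reactivity is 1 − 0.566×0.3 = 0.83, so variance = 36.1 + 0.83²×21 = 50.6. Pooled SD = √53.85 = 7.34.
- Effective d = 3.31/7.34 = 0.45, which at n = 50 gives 61% power.

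Simulated power (10,000 runs) for CV 0.3 / 0.4 / 0.5, error SD as a share of the full response:

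| Error SD | Raw change | Unweighted change per mm Hg |
|---|---|---|
| 0 | 0.61 / 0.68 / 0.72 | 0.80 / 0.79 / 0.80 |
| 10% | 0.56 / 0.65 / 0.69 | 0.72 / 0.76 / 0.77 |
| 20% | 0.49 / 0.58 / 0.64 | 0.57 / 0.65 / 0.70 |

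**5. False positives with unequal early stopping.** Same model, no true difference, no error.
- 40% versus 20%: the mean rise differs by (0.40−0.20)×10 = 2 mm Hg. Raw change reaches p<0.05 in 26 / 18 / 15% of studies. Per mm Hg the rate is about 5%.
- 30% versus 25%: the gap is 0.05×10 = 0.5 mm Hg, and raw change reaches p<0.05 in 5–6% of studies.

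**6. Which adjustment.** Step 4 puts every early stop at 55 mm Hg, which favours a simple ratio. Because sleep has no floor, the early-stop rises were instead spread uniformly over 2–22.5 mm Hg, with 30% early stops in both groups. Power for CV 0.3 / 0.5:

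| Error SD | Raw change | Unweighted ratio | CO2 rise as covariate |
|---|---|---|---|
| 10% | 0.50 / 0.66 | 0.65 / 0.73 | 0.71 / 0.75 |
| 20% | 0.42 / 0.61 | 0.42 / 0.58 | 0.59 / 0.68 |

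At 20% error the unweighted ratio gains nothing over raw change. At CV 0.3 a slope weighted by dose does about as well as the covariate (about 58%).

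**The case against.** **The plan is silent rather than wrong.** It gives no formula for the change in CBF, it speaks of CBF regulation and response to hypercapnia, and its covariate list is open. A reader might infer that the sponsor decided to disregard achieved CO2. The text does not support that. What stands is that neither the endpoint nor the named model terms contain CO2, and leaving stimulus size to a later choice is not pre-specification.

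**Sleep may carry less weight.** It is in the synopsis primary objective, but sections 2.1, 6.1 and 6.4.2 do not mention it. Applying the 50-per-group design to sleep is therefore an assumption. This limits the point's reach but does not remove it.

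**Group bias is conjecture.** A reader might infer that a blunted sleep response in OSAS would be an artefact of earlier arousal. The documents give no early-stop rates or achieved CO2 by group, and step 5 shows that a small imbalance does almost nothing. Bias is possible, not shown.

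**The averaging mismatch is not unique to sleep.** The awake test also lasts under 5 minutes. The 75% figure applies only if the averaging rule is used for sleep, which the text does not say outright. It remains true that no other rule is given.

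**The obvious remedies have faults.** The unweighted ratio is unstable for small rises. The mixed models in 6.4.2 are an alternative to GEE for change across visits, so they do not already supply a within-challenge slope. Both objections stand and shape the fix.

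**Conclusion.** The point holds as a gap in definition that should be closed. The sleep challenge has no common dose, the analysis names no CO2 term, and the averaging window does not fit.

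The firmest consequence is lost power: 61–72% instead of about 80% with 30% of challenges in both groups ending at 55 mm Hg and no measurement error. The gain from adjustment shrinks as measurement error grows. These figures assume a linear response, baseline 42.5 mm Hg, between-child CV 0.3–0.5 and 50 evaluable sleep studies per group. Early-stop rates and evaluable sleep numbers are not in the documents.

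Bias is conditional. At 40% versus 20% early stops the raw change gives 15–26% false positives; at 30% versus 25% it stays at 5–6%. The documents do not show which case applies, or in which direction.

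A reader might also infer that sleep needs the awake test's 55 mm Hg floor, or that OSAS children should be retested after surgery at their pre-operative pressure. Neither follows. With one attempt per stage, a floor would drop the children who arouse early. The treating pressure is needed at baseline, and repeating it once OSAS has resolved is a debatable trade-off. The supported conclusion on pressure is narrower: the sleep difference between OSAS and controls cannot be fully separated from test pressure, and the size of any pressure effect is unknown.

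**What to change.** In 5.1.3 and 6.4.2:

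1. Define the sleep CBF response from the pre-challenge baseline and the CO2 exposure period of that challenge, in place of the four-of-five-minute average.
2. Account for achieved CO2 by one method named in advance: either a within-challenge slope of CBF on end-tidal CO2, weighted so that short challenges count less, or the CBF change with the end-tidal CO2 rise as a covariate. Do not use an unweighted ratio per mm Hg. Use the chosen method for the group and the before/after comparisons.
3. Use end-tidal CO2 throughout, with transcutaneous CO2 only as a sensitivity analysis.
4. Keep challenges ended by arousal, report the raw change alongside, and tabulate stop reason, achieved PCO2 and applied pressure by group and visit.
5. State that the sleep OSAS-versus-control difference cannot be fully separated from test pressure.

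The cost is low. Both CO2 signals are already monitored during CBF testing, so no visit, procedure or exclusion is added. The work is one outcome definition, one model term or slope, and one table. The downside is that the adjustment assumes a roughly linear CBF–CO2 response, which is why the raw change should stay in the report.
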